5.1 Duration

For each phase, individual subject participation is expected to be approximately 135 days through the study period.

5.2 Rationale

Previous clinical investigations have confirmed the safety and clinical performance of the 780G insulin pump when used in a type 1 population in subjects 7 years of age or older. This investigation is intended to provide confirmation of the safety and clinical performance of the 780G system in a type 2 population in subjects 18-80 years of age.

6. Determination of Sample Size

A total of up to 575 subjects with insulin-requiring type 2 diabetes age 18-80 will be enrolled collectively in Phase 1 and Phase 2 at up to 40 investigational centers across the United States with at least 300 subjects entering the study period of Phase 2.

A maximum of 40 subjects may be enrolled, not inclusive of screen failures, at each investigational center.

The following sample sizes support the evaluation of the MiniMed™ 780G insulin pump with Guardian 4 Sensor and the MiniMed™ 780G BLE 2.0 insulin pump with Disposable Sensor 5 (DS5), separately.

- [REDACTED]
- [REDACTED]
[REDACTED]
[REDACTED]
[REDACTED]
[REDACTED]
 - [REDACTED]
[REDACTED]
[REDACTED]
[REDACTED]
[REDACTED]
 - [REDACTED]
[REDACTED]
[REDACTED]
[REDACTED]
[REDACTED]

7. Statistical Methods

7.1 Study Subjects

7.1.1 General Aspects of Analysis

For each phase, all data collected from the time of screening until the end of the study will be collected on eCRFs, subject questionnaires, and electronically by uploading the various devices. For each phase, data and analyses will be summarized in a Clinical Study Report. Any deviations from the original statistical plan and the rationale will be described in the Clinical Study Report.

7.1.2 Disposition of Subjects

For each phase, the number of subjects enrolled, completed, and early terminated in the study will be presented. The reasons for discontinuing prior to study completion will be summarized by period.

7.1.3 Clinical Investigation Plan (CIP) Deviations

For each phase, all protocol deviations will be presented in listings.

7.1.4 Analysis Sets

For each phase, the following populations will be analyzed.

- Intention to Treat (ITT) Population
The Intention to Treat (ITT) population will include all subjects who start the study period. Primary safety, primary effectiveness, secondary effectiveness, and descriptive endpoints will be evaluated for the ITT population.
- Per Protocol (PP) Population
The Per Protocol (PP) population will include all subjects who complete the study period, are in SmartGuard $\geq 80\%$ of the time, and without major deviations. Primary safety, primary effectiveness, and secondary effectiveness endpoints will be evaluated for the PP population as the sensitivity/supplementary analyses.
- Safety Population
The Safety Population will include all enrolled subjects (subjects who signed the informed consent form). Safety adverse events data summary will be evaluated for the safety population.

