8.2 Subject Enrollment

Subjects will be considered enrolled in the study upon signing the ICF.

A subject will be assigned a unique study subject ID via the eCRF, which is a 9-digit code (341XXXXXX). The first three digits refer to the CIP number (341), the next three digits refer to the investigational center number, and the last 3 digits refer to the subject number assigned during Visit 1 (e.g., 341002001 is subject 001 from investigational center 002).

The investigator will maintain a log of all subjects enrolled in the clinical study, assigning a subject ID linked to their names, and alternative subject ID.

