12.2 Data Monitoring Committee

A data monitoring committee (DMC) consisting of external physicians with an expertise in Endocrinology and the management of insulin-requiring diabetes including CGM, along with an external statistician will be convened to review study progress and safety. The Board will convene approximately every 90 days. The Board will also meet when ad hoc review is required.

The DMC will perform 4 main functions:

First: DMC will track and trend the overall safety of the study.

Event rate, defined as number of events per 100 patient years will be reviewed by the DMC with respect to the following:

- Event rate of all SAEs
- Event rate of severe hypoglycemia
- Event rate of severe hyperglycemia
- Event rate of DKA
- Event rate of HHS
- Event rate of device related AEs

Second: Based on their meetings, DMC will recommend a decision to the sponsor regarding the following:

- Whether or not enrollment should be halted.
- Whether or not the entire study will need to be stopped including for those subjects who have received study devices already.

Note: If it is decided to withdraw subjects from participation in the study or if the study is stopped, subjects will be followed-up in accordance with standard practice by their own providers.

Third: During the study, the following steps will be taken for:

- UADE

- Device related DKA
 - Device related HHS
 - Device related Severe Hypoglycemia
1. Investigational center staff will notify the sponsor within approximately 24 hours of investigator or study coordinator awareness of events described above.
 2. Sponsor will notify the FDA within approximately 3 business days of awareness of the event and provide updates to the agency as information becomes available.
 3. DMC is to meet within 10 business days from CEC adjudication of the event. The investigator should be available to answer questions from DMC, as needed.
 4. Based on their review, DMC will recommend that the sponsor make a decision regarding the following:
 - a) Whether or not subject enrollment may continue
 - b) Whether or not new subject enrollment should be suspended, with enrolled subjects continuing in the study.
 - c) Whether or not the entire study should be stopped, including those subjects who have already received study devices.

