7.3.1.8 Safety Data Summarized

- Serious Adverse Events (SAE)
- Serious Adverse Device Effects (SADE)
- Unanticipated Adverse Device Effects (UADE)
- Incidence of Severe Hypoglycemia
- Incidence of Severe Hyperglycemia
- Incidence of DKA
- Incidence of HHS

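### The SAP reports adverse-event incidence by period but names only the all-consented set as its population; read that way, study-period incidence would be understated by the fraction lost before Visit 9

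*SAP*

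**What the plan says.** **Population.** SAP 7.1.4: "The Safety Population will include all enrolled subjects (subjects who signed the informed consent form"). The same section adds: "Safety adverse events data summary will be evaluated for the safety population". Protocol 8.2 fixes the meaning of enrolled: "Subjects will be considered enrolled in the study upon signing the ICF". Eligibility, including laboratory results, is confirmed only at Visit 2 (Protocol 9.1.1 and Table 3), so screen failures belong to this set. The SAP removes them explicitly in one place only, the site cap in section 6: "A maximum of 40 subjects may be enrolled, not inclusive of screen failures, at each investigational center".

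**Outputs.** "Incidence of Severe Hypoglycemia" and the matching items for severe hyperglycemia, DKA and HHS appear under the study period (SAP 7.3.1.8), run-in (7.3.2.3) and continued access (7.3.3.2). A note in 7.3.2.3 assigns certain events of transitioned subjects to the Phase 2 run-in, so numerators are split by period. SAP 7.2 presents categorical data as counts and percentages.

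**Alternatives already in the documents.** The ITT set in SAP 7.1.4 consists of those who start the study period, but it is assigned to the primary, secondary and descriptive endpoints and not to adverse events. Protocol 12.2 has the DMC review an exposure-based measure: "Event rate, defined as number of events per 100 patient years". The visible SAP does not carry that measure into the report.

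**The concern.** The numerator is specific to a period and the only population named for the summary is not. A subject who fails screening, or who leaves during run-in, cannot have a study-period event but would still be counted in the denominator of study-period incidence. In the same way, run-in incidence would count people who never received a study pump, and continued-access incidence would count Phase 1 subjects who never entered it.

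The error runs in one direction: it makes the device look safer. It matters because the primary safety endpoint is change in HbA1c (SAP 7.3.1.1), so acute harms such as severe hypoglycemia and DKA are assessed through these descriptive summaries, in a study meant to support a labeling submission (SAP 3.2). The events are likely to be few, and a reader will look at the percentage and perhaps an upper confidence limit.

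**Working it through.** There is no planned figure to reproduce. The visible text gives no expected event rate, screen-failure rate or run-in loss, and the sample-size derivation is redacted.

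**Inputs**
- Starters, n = 300. SAP section 6: "at least 300 subjects entering the study period of Phase 2". This is a minimum.
- Loss between consent and Visit 9, a: not given. Assumed 5% to 40%.
- Ceiling on enrollment, both phases together: "A total of up to 575 subjects with insulin-requiring type 2 diabetes age 18-80 will be enrolled collectively" (SAP section 6).

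**Formula.** With x affected subjects and N consented, where a = 1 − n/N:

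reported incidence = x/N = (x/n) × (n/N) = incidence among starters × (1 − a)

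The relative understatement is therefore a itself, whatever x is.

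| Assumed loss a | Consented N = 300/(1 − a) | 300/N | 3 affected subjects as % of N |
|---|---|---|---|
| 0 (starters only) | 300 | 1.00 | 1.00% |
| 5% | 316 | 0.95 | 0.95% |
| 10% | 333 | 0.90 | 0.90% |
| 20% | 375 | 0.80 | 0.80% |
| 30% | 429 | 0.70 | 0.70% |
| 40% | 500 | 0.60 | 0.60% |

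At a = 40% the incidence among starters is 1/0.60 = 1.67 times the reported figure. The extreme arithmetic bound is 300/575 = 0.52. It is not realistic for Phase 2, because 575 also covers Phase 1 and the Phase 1 share is not visible. Even N = 500 would leave only 575 − 500 = 75 for Phase 1 if each subject counts once.

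**Effect on an interval, if one is shown.** SAP 7.2 makes confidence intervals two-sided 95% where needed. Exact (Clopper-Pearson) limits for three affected subjects are 0.21% to 2.89% on 300, 0.17% to 2.32% on 375, and 0.12% to 1.74% on 500. With no events the upper limit is 1 − 0.025^(1/n): 1.22%, 0.98% and 0.74%.

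**Exposure-based rate.** The study period lasts about 90 days, so 300 starters contribute 300 × 90/365.25 = 73.9 patient-years. Screen failures add nothing if only study-period time is counted. If time ran over the whole participation of about 135 days, the total would be 300 × 135/365.25 = 110.9 patient-years, and a study-period rate would be 73.9/110.9 = 0.67 of its proper value. The patient-time must therefore match the period as well.

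**Run-in and continued access.** Transitioned subjects did not have to complete Phase 2 Visits 2 to 8 (SAP section 5), yet SAP 7.3.2.3 counts their events between Phase 2 consent and the study period as run-in. A run-in denominator based on Visit 2 alone would include those events and leave those subjects out. Continued-access visits recur every 90 days until the sponsor ends the study, and subjects may exit or transition (Protocol 18.4.2). Follow-up is thus unequal, and a percentage alone describes it poorly.

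**The case against.** The strongest objection is that dilution is inferred. A reader might conclude that the reported rates *are* understated. The documents do not establish that: neither defines incidence, and SAP 7.2 leaves table layout to a separate TLF document. If the tables show event counts, a percentage of subjects entering the period, or a rate on period-specific patient-time, screen failures cause no dilution. This stands as a limit on the wording. It does not remove the point, because SAP 7.1.4 names a population for these summaries and nothing visible replaces it.

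It also stands that an all-consented set is legitimate for listing, since adverse events are collected from consent (Protocol 11.1). No event is lost, and a careful reader could recompute study-period percentages from the ITT count.

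Three further inferences should be resisted:
- *Screen failure differs between the phases and distorts their comparison.* Neither document gives a screen-failure rate for either phase, and the phases are evaluated separately.
- *These are the trial's only direct safety figures.* The CEC adjudicates events, the DMC reviews rates, device deficiencies are summarized, and part of the endpoint text is redacted.
- *Everyone who left before Visit 9 was unexposed to SmartGuard.* Subjects already on a Medtronic pump in Auto Mode use it in run-in with Auto Correction off (SAP section 5). The accurate description is that they did not enter the study period.

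**Conclusion.** The point holds in conditional form. On the natural reading of SAP 7.1.4 with 7.2 and 7.3.1.8, study-period incidence would be understated by exactly the fraction of consented subjects lost before Visit 9. The 5% to 40% range is illustrative: it rests on assumed attrition and on the minimum of 300 starters, and the documents support no particular value. Transitioned subjects skip the run-in visits, so run-in loss does not apply to them.

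The consequence is confined to descriptive safety reporting. The primary safety endpoint is evaluated in the ITT set, and no hypothesis test, alpha or power changes. The change is still worth making, because the direction favors the device and the SAP already contains a better denominator.

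**What to change.** In SAP 7.1.4, keep the all-consented set for listing every adverse event from consent. In 7.1.4 and in 7.3.1.8, 7.3.2.3 and 7.3.3.2, define incidence as subjects with an event divided by subjects entering that period:
- **Study period:** the existing ITT set.
- **Run-in:** subjects who started run-in at Visit 2. For transitioned subjects' events between Phase 2 consent and the study period, either report them separately or add those subjects to the denominator, and state which.
- **Continued access:** subjects who entered it.
- **Consent to Visit 2:** list events separately.

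Report events per 100 patient-years alongside, counting only exposure within the period concerned, and align the TLF templates.

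The cost is SAP wording and table denominators, with no new data collection. Reported percentages will be higher than on the all-consented set: by a factor of 1/0.95 = 1.05 at 5% loss, and 1.67 at 40%.

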7.2 General Methodology

The following will be evaluated by phase.

For each phase, summary statistics will be represented by number of subjects (n), mean, median, and standard deviation for continuous variables and by counts and percentages for categorical variables. P-values for hypothesis testing will be evaluated based on one-sided testing using a significance level of 0.025. Confidence intervals, if needed, will be reported as two-sided 95% confidence intervals. For primary safety, primary effectiveness, and secondary effectiveness endpoints, normality will be verified for appropriate statistical methodology. For testing the statistical significance of the difference, comparisons between the outcomes in the study period and the threshold will be performed using a one-sample t-test if the normality assumption is met or a Wilcoxon signed rank test if the normality assumption is not met.

The templates for Tables, Listings, and Figures (TLFs) by phase will be available in the TLFs document.

7.2.1 Center Pooling

For each phase, data will be pooled for analysis at the subject level. Additional sensitivity analysis will be performed for site effect in section 7.3.1.4.

7.2.3 Adjustments for Multiple Comparisons

For each phase, a fixed-sequence statistical strategy will be applied for primary and secondary endpoints to adjust for multiplicity and the order of the tests will be as follows: 1. Primary effectiveness and safety endpoints and 2. Secondary effectiveness endpoint. Further testing stops as soon as there is a failure of an endpoint in the sequence to show significance at level alpha (e.g., $\alpha = 0.025$).

7.2.4 Demographic and Other Baseline Characteristics

For each phase, subject characteristics, including age, gender, race, ethnicity, medical diagnosis, height, weight, BMI, and baseline HbA1c will be summarized by descriptive statistics (mean, standard deviation, minimum, median, and maximum) for continuous variables and by counts and percentages for categorical variables.

7.2.5 Treatment Characteristics

Not applicable.

7.3 Evaluation of Objectives

The following endpoints will be evaluated for each of the phases, separately.

Phase 1: MiniMed™ 780G insulin pump with Guardian 4 Sensor

Phase 2: MiniMed™ 780G BLE 2.0 insulin pump with DS5

All effectiveness endpoints will be analyzed using the data from Visit 16 to the end of the study period (Auto Basal target set at investigator's discretion).

7.3.1 Study Period

7.3.1.1 Primary Safety Endpoint

The overall mean change in HbA1c, $\Delta\mu_{780G}$, from baseline to end of 3-month study period will be estimated and compared by a non-inferiority test to the threshold of 0% with a margin of 0.4%. A significance level of 0.025 (one-sided) will be used.

The hypothesis of non-inferiority is mathematically expressed as:

$$H_0: \Delta\mu_{780G} \geq 0\% + 0.4\%$$

$$H_a: \Delta\mu_{780G} < 0\% + 0.4\%$$

Note: Phase 1 subjects transitioned into Phase 2 will not be included in this analysis for Phase 2.

The null hypothesis will be tested against the alternative hypothesis using a one sample t test if the normality assumption is met or a Wilcoxon signed rank test if the normality assumption is rejected. The overall mean change in HbA1c from baseline to end of 3-month study period is less than 0% with a margin of 0.4% will be concluded if the null hypothesis is rejected.

7.3.1.2 Primary Effectiveness Endpoint

The mean % of time in range (TIR 70-180 mg/dL), μ_{780G} , will be estimated and compared by a non-inferiority test to the threshold of 70% with a margin of 7.5%. A significance level of 0.025 (one-sided) will be used.

The hypothesis of non-inferiority is mathematically expressed as:

$$H_0: \mu_{780G} \leq 70\% - 7.5\%$$

$$H_a: \mu_{780G} > 70\% - 7.5\%$$

The null hypothesis will be tested against the alternative hypothesis using a one sample t test if the normality assumption is met or a Wilcoxon signed rank test if the normality assumption is rejected. The mean % of time in range is greater than 70% with a margin of -7.5% will be concluded if the null hypothesis is rejected.

7.3.1.6 Device Deficiencies

Descriptive summary will be used to characterize device deficiencies:

- All reports of device issues.

7.3.1.7 Subject Feedback

Descriptive summary will be used to characterize study questionnaire results. Refer to CIP341 Questionnaire Guide for administration details.

7.3.1.8 Safety Data Summarized

- Serious Adverse Events (SAE)
- Serious Adverse Device Effects (SADE)
- Unanticipated Adverse Device Effects (UADE)
- Incidence of Severe Hypoglycemia
- Incidence of Severe Hyperglycemia
- Incidence of DKA
- Incidence of HHS

7.3.2 Run-in Period**7.3.2.1 Device Deficiencies**

Descriptive summary will be used to characterize device deficiencies:

- All reports of device issues.

7.3.2.2 Subject Feedback

Descriptive summary will be used to characterize study questionnaire results. Refer to CIP341 Questionnaire Guide for administration details.

7.3.2.3 Safety Data Summarized

- Serious Adverse Events (SAE)
- Serious Adverse Device Effects (SADE)
- Unanticipated Adverse Device Effects (UADE)
- Incidence of Severe Hypoglycemia
- Incidence of Severe Hyperglycemia
- Incidence of DKA
- Incidence of HHS

Note: For subjects participating in both Phase 1 and Phase 2, if there is an AE within the time between Phase 2 consent and Phase 2 study period, it will be attributed to the Phase 2 run-in period.

7.3.3 Continued Access Period

Only applicable for Phase 1.

7.3.3.1 Device Deficiencies

Descriptive summary will be used to characterize device deficiencies:

- All reports of device issues.

7.3.3.2 Safety Data Summarized

- Serious Adverse Events (SAE)

- Serious Adverse Device Effects (SADE)
- Unanticipated Adverse Device Effects (UADE)
- Incidence of Severe Hypoglycemia
- Incidence of Severe Hyperglycemia
- Incidence of DKA
- Incidence of HHS

7.4 Health Outcomes Analyses

For each phase, descriptive summary will be used to characterize data from questionnaire results.

